#### **5.3.1.2 Collection and Handling of Pharmacodynamic Variables**

Instructions on preparation and shipment of pharmacodynamic samples will be provided by a certified laboratory or the sponsor outside this protocol.

#### **5.3.1.3 Disease Response Biomarkers**

Blood samples will be collected at time points specified in [Table 2](#). The panel may include but is not limited to: IL-6, IL-1, TNF $\alpha$ , CXCL13, CXCL10, CRPM, C3M, C1M, MMP-3 and CTX-I. The fasting status will be recorded in the study source documentation. Separate instructions for the collection, handling and shipping of disease response biomarkers will be provided outside of the study protocol.

## **5.3.2 Drug Concentration Measurements**

### **5.3.2.1 Collection of Samples for Analysis**

A single pharmacokinetic sample will be collected at study visits BL, Weeks 6, 12, 24, 36, 48, 72, and 96 without regard to the time of dosing. Blood samples for PK will be collected at any time during the visit, and preferably within 1 to 8 hours after the last dose. The exact date, time and number of capsules of the last 2 doses of study drug taken prior to the pharmacokinetic sample collection will be recorded to the nearest minute starting with the dose prior to PK collection.

Blood samples for assay of upadacitinib will be collected in 3 mL K2EDTA containing tubes by venipuncture. Refer to the study specific laboratory manual for detailed instructions on sample collection, processing, and shipment.

### **5.3.2.2 Measurement Methods**

Plasma concentrations of upadacitinib will be determined by the Drug Analysis Department at AbbVie using a validated liquid chromatography/mass spectrometry method.

## **5.3.3 Efficacy Variables**

ACR20/50/70 response rates at Weeks 6, 12, 24, 36, 48, 60, 72, 84, 96 and every 24 weeks thereafter until the end of the study will be evaluated based on 20/50/70% improvement in TJC, SJC, and  $\geq 3$  of the 5 measures of Patient's Assessment of Pain (VAS), Patient's Global Assessment of Disease Activity, Physician's Global Assessment of Disease Activity, Health Assessment Questionnaire Disability Index (HAQ-DI), and hsCRP. Change from Baseline in individual ACR components at Weeks 6, 12, 24, 36, 48, 60, 72, 84, 96 and every 24 weeks thereafter until the end of the study will also be evaluated: TJC, SJC, Patient's Assessment of Pain (VAS), Patient's Global Assessment of Disease Activity, Physician's Global Assessment of Disease Activity, hsCRP, and Health Assessment Questionnaire Disability Index (HAQ-DI). Baseline data for each subject

will be the data collected at the visit immediately prior to starting treatment with active upadacitinib (this visit could be in RCT or OLE).

The proportion of subjects achieving Low Disease Activity (LDA) or Clinical Remission (CR), and the proportion of subjects achieving CR will be evaluated at Weeks 6, 12, 24, 36, 48, 60, 72, 84, 96 and every 24 weeks thereafter until the end of the study. The criteria will be based on DAS28 [CRP] or CDAI as follows:

	DAS28 [CRP]	CDAI
LDA	$2.6 \leq \text{to} < 3.2$	$2.8 < \text{to} \leq 10$
CR	$< 2.6$	$\leq 2.8$

Change from Baseline in DAS28 [CRP] disease activity score, CDAI and Patient Reported Outcomes including FACIT-Fatigue Scale, RA-WIS, and EQ-5D will be analyzed at Weeks 6, 12, 24, 36, 48, 72, 96 and every 24 weeks thereafter until the end of the study.

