**Statistical Methods:**

**Efficacy:**

Baseline data for each subject will be the data collected at the visit immediately prior to starting double-blind treatment.

The response rates of ACR20/50/70 will be summarized with 95% confidence intervals by visit.

Change from Baseline will be summarized with descriptive statistics for TJC, SJC, Patient's Assessment of Pain, Patient's Global Assessment of Disease Activity, Physician's Global Assessment of Disease Activity, HAQ-DI, hsCRP, DAS28[CRP], CDAI, and Patient Reported Outcomes, including FACIT Fatigue Scale, RA-WIS and EQ-5D by visit.

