**Statistical Methods (Continued):**

**Efficacy (Continued):**

The proportion of subjects achieving LDA ( $2.6 \leq \text{DAS28 [CRP]} < 3.2$  or  $2.8 < \text{CDAI} \leq 10$ ) or CR ( $\text{DAS28 [CRP]} < 2.6$  or  $\text{CDAI} \leq 2.8$ ), and the proportion of subjects achieving CR ( $\text{DAS28 [CRP]} < 2.6$  or  $\text{CDAI} \leq 2.8$ ) will be summarized with 95% confidence intervals by visit.

In an alternate assessment for summarizing the response rates, baseline data will be assumed to be the data collected at the visit immediately prior to starting treatment with active upadacitinib.

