#### **8.1.3 Baseline Characteristics**

For analyses purposes, baseline data for each subject will be the data collected at the visit immediately prior to starting double-blind treatment. In an alternate assessment for summarizing the safety and laboratory data, baseline data will be assumed to be the data collected at the visit immediately prior to starting treatment with active upadacitinib.

Demographic variables such as age, gender, race, height, weight, BMI, race, ethnicity, duration of disease, vital signs (blood pressure, heart rate, and temperature), and planned efficacy assessments such as the counts for both SJC and TJC, Patient's Assessment of Pain (VAS), Patient's Global Assessment of Disease Activity, Physician's Global Assessment of Disease Activity, Patient's Assessment of Physical Function by Health Assessment Questionnaire – Disability Index (HAQ-DI), and hsCRP will be summarized at Baseline.

Summary statistics for continuous variables will include the number of observations, mean, standard deviation, median, and range. For other discrete variables, frequencies and percentages will be computed in each category.

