## **8.1.6 Safety Analysis**

### **8.1.6.1 General Considerations**

All subjects who receive at least one dose of upadacitinib in this OLE study will be included in the safety analysis. Incidence of adverse events, serious adverse events, premature discontinuation, and changes from Baseline in vital signs, physical examination results, and clinical laboratory values will be analyzed by visit. Treatment-emergent adverse events will be tabulated by system organ class and by MedDRA preferred term. Mean change from Baseline for laboratory and vital signs data will be summarized by visit. For analyses purposes, baseline for vital signs, physical examination results, and clinical laboratory results for subjects will be the data collected at the visit immediately prior to starting double-blind treatment. In an alternate assessment for summarizing the safety and laboratory data, baseline data will be assumed to be the data collected at the visit immediately prior to starting treatment with active upadacitinib.

Incidence of adverse events, changes in vital signs, physical examination results, and clinical laboratory values will be analyzed.

Treatment emergent adverse events will be tabulated by system organ class (SOC) and by the Medical Dictionary for Regulatory Activities (MedDRA) preferred term. Mean change from baseline for laboratory and vital signs data will be summarized by visit.

Missing safety data will not be imputed.

The impact of time between completion of RCT and roll-over to OLE will be explored.

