5.2 Definition of Baseline

The baseline value will be determined by the last non-missing measurement recorded on or before the date of the first dose of study drug in RCT. This applies to both efficacy and safety analysis.

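### The protocol defines the efficacy baseline two ways, and the SAP leaves out the alternate baseline the protocol promises, so change before any upadacitinib cannot be separated out for subjects first treated in the OLE

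*Protocol*

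**What the plan says.** **Protocol, main definition.** The efficacy part of the synopsis's Statistical Methods says: "Baseline data for each subject will be the data collected at the visit immediately prior to starting double-blind treatment". Section 8.1.3 repeats this for analysis purposes generally: "baseline data for each subject will be the data collected at the visit immediately prior to starting double-blind treatment". Section 8.1.6.1 applies the same visit to vital signs, physical examination and laboratory results. The joint-count improvement formula in Section 8.1.5.1 also counts from Day 1 of the RCT.

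**Protocol Section 5.3.3.** Here the only efficacy baseline given is the visit "immediately prior to starting treatment with active upadacitinib (this visit could be in RCT or OLE".

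**Protocol, alternate definition.** The synopsis adds, for efficacy: "In an alternate assessment for summarizing the response rates, baseline data will be assumed to be" those from the visit before active upadacitinib began. Section 8.1.3 adds, for safety: "In an alternate assessment for summarizing the safety and laboratory data, baseline data will be assumed to be" those from that same visit. The safety part of the synopsis and Section 8.1.6.1 say the same. Section 8.1.5 does not carry the response-rate alternate.

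**SAP Section 5.2.** Baseline is the last available value up to the first RCT dose. "This applies to both efficacy and safety analysis". No alternate appears there or anywhere else in the main-study SAP.

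**The concern.** All subjects start the OLE on the same dose whatever they received in the RCT (Protocol Section 5.6). For a subject already on upadacitinib in the RCT, the two baselines should be the same visit. For a subject first given active drug in the OLE they are different visits, and change from the RCT baseline is the sum of two parts: change before any upadacitinib and change on it.

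That sum enters ACR20/50/70, change from baseline in the ACR components, DAS28, CDAI, SDAI and patient-reported outcomes, laboratory mean changes and shifts, and the blood pressure and weight criteria in SAP Table 7. It also enters the haemoglobin and creatinine grades that are defined relative to a pre-treatment or baseline value. The alternate assessment was the protocol's way of showing how much this matters. Without it, a reader of the long-term tables cannot tell the two parts apart.

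**Working it through.** The plan states no figure that depends on this point, so there is none to reproduce. The check has three parts.

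**1. Definitions side by side**

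| Place | Main baseline | Alternate |
|---|---|---|
| Protocol synopsis, efficacy | Before double-blind treatment | Before active drug, response rates |
| Protocol synopsis, safety | Before double-blind treatment | Before active drug |
| Protocol 5.3.3 | Before active drug | None |
| Protocol 8.1.3 | Before double-blind treatment | Before active drug, safety and laboratory |
| Protocol 8.1.6.1 | Before double-blind treatment | Before active drug, safety and laboratory |
| SAP 5.2 | Before first RCT dose | None |

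Section 5.3.3 is the outlier on the main definition. The SAP is the outlier on the alternate.

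**2. Does another main-study output fill the gap?**

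- SAP Table 1 has no OLE-entry row: its Baseline is the RCT value and the Week 6 window opens on Day 2.
- Efficacy results and laboratory and vital-sign mean changes are grouped by titration sequence (SAP 9.1, 10.1), not by RCT arm.
- The MMRM and GLMM include parent study as a factor but not RCT arm (SAP 9.1.1).

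None of these separates RCT-period change from open-label change. The pre-OLE stretch is at least 12 weeks, because entry follows the RCT Week 12 visit by up to 30 days. I put no firm upper limit on it, since Protocol Section 3.1 describes the RCTs as 12–24 weeks.

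**3. Illustrative size**

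For one subject, improvement = (baseline − current) / baseline. Invented joint counts at RCT baseline, OLE entry and a later OLE visit:

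- 25, 20, 18: from RCT baseline (25 − 18)/25 = 28%; from the pre-active visit (20 − 18)/20 = 10%. The 20% joint criterion is met on the first and missed on the second.
- 20, 24, 18: from RCT baseline (20 − 18)/20 = 10%; from the pre-active visit (24 − 18)/24 = 25%. The result reverses.

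For all subjects together, let f be the share with no active drug in the RCT, r the net share of those whose ACR status changes with the baseline, and d their mean RCT-period change in DAS28. The documents give none of these; all three are assumptions. Enrolment is 494 (SAP 4.2).

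- f = 10% to 33% is 0.10 × 494 = 49 to 0.33 × 494 = 163 subjects.
- Shift in an ACR rate = f × r: 0.10 × 0.10 = 1.0 point to 0.33 × 0.30 = 9.9 points.
- Shift in mean DAS28 change = f × d, with d from −0.3 to −1.0: 0.10 × (−0.3) = −0.03 to 0.33 × (−1.0) = −0.33 units. Among the affected subjects alone the shift is the whole of d.
- For scale, the 95% CI half-width for a 70% rate (assumed) is 1.96 × √(0.7 × 0.3 / 494) = 4.0 points.

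The SAP reports efficacy by titration sequence, so the shift in a given table depends on f and r within that sequence.

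**The case against.** An RCT baseline is a legitimate main choice and was made deliberately: the SAP's Version 3.0 change summary states it for both efficacy and safety. It matches the joint-count formula and the RCT-baseline reference used throughout the study design. The study has no comparator arm and plans no tests. LDA and CR use absolute thresholds, and TEAEs are anchored to the first open-label dose, so neither moves. All of this stands, and it is why the RCT baseline should stay. It does not reconcile Section 5.3.3, and it does not explain why an analysis still promised in the protocol is missing from the SAP. The change summary says nothing about the alternate.

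A second objection also stands. A pooled alternate-baseline table would be hard to read, because OLE Week 6 would be about 6 weeks from baseline for some subjects and at least 18 weeks for others. The alternate needs a split by when active drug was first received.

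Three stronger readings are tempting, and the documents do not support them:

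- *A reader might infer that a known placebo group inflates the results.* Neither document says that M13-537 or M13-550 had a placebo arm, or how many such subjects rolled over. That some subjects first received active drug in the OLE is inferred from Section 5.3.3, which allows the pre-active visit to fall in the OLE, and from the existence of the alternate baseline.
- *A reader might multiply an assumed share by the proportion already at ACR20 on OLE entry* (for example 15% × 35% = 5 points, or 25% × 60% = 15 points) and call the product the overstatement. That counts early responders. Some of them would also respond against the later baseline, so only the net change in status matters. The documents supply neither input.
- *A reader might infer that the SAP contradicts the protocol's main analysis.* The synopsis and Section 8 agree with the SAP there; the conflict over the main definition comes from Section 5.3.3.

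**Conclusion.** The point holds as a documentation conflict together with an unexplained omission. Protocol Section 5.3.3 disagrees with the synopsis and Section 8.1.3 on the efficacy baseline, and the SAP lacks the alternate assessment that the protocol promises for response rates and for safety and laboratory data. If any subjects first took upadacitinib in the OLE, their baseline-relative results mix pre-drug and on-drug change, and the planned main-study outputs cannot separate the two.

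Neither size nor direction can be fixed from the documents. The range of about 1–10 points in an overall ACR rate rests entirely on the assumed 10–33% and 10–30%. Improvement during the RCT raises the apparent open-label effect; worsening lowers it. This should be corrected, but it does not undermine the choice of RCT baseline as the main definition.

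**What to change.** 1. Correct Protocol Section 5.3.3 so that its efficacy baseline is the visit before double-blind treatment, in line with the synopsis and Section 8.1.3.
2. In SAP Section 5.2, keep the RCT baseline as the main definition and add the protocol's alternate: the latest non-missing value up to the first dose of active upadacitinib, whether in the RCT or the OLE. Apply it to response rates and to laboratory and vital-sign changes.
3. Show these results beside the main tables, split by whether active drug was first received in the RCT or the OLE.

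The cost is SAP wording and one extra set of descriptive tables. No new data are needed: under footnote a of Protocol Table 2, RCT Week 12 results serve as OLE Week 0 for subjects who enrol within 14 days, and the Week 0 procedures are repeated for those who enrol later.

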### 5.3.4 Safety Variables

Incidence of adverse events, changes in vital signs, physical examination results and clinical laboratory data will be assessed throughout the study.

### 5.3.5 Pharmacokinetic Variables

Plasma upadacitinib concentrations will be determined at the times indicated in [Table 2](#). A mixed-effects modeling approach may be used to estimate the population central value and the empirical Bayesian estimates of the individual values for upadacitinib oral clearance (CL/F) and volume of distribution ( $V_{ss}/F$ ). Additional parameters may be estimated if useful in the interpretation of the data.

### 5.3.6 RA Disease Response Biomarkers Variables

Subjects will have additional blood samples collected to assess disease response. Samples will be analyzed for measurement of non-genetic markers related to disease

activity/prognosis of RA, autoimmunity/inflammation, and/or response to upadacitinib. The panel may include but is not limited to: IL-6, IL-1, TNF $\alpha$ , CXCL13, CXCL10, CRPM, C3M, C1M, MMP-3 and CTX-I.

Change from Baseline in RA disease response biomarkers at Weeks 6, 12, 24 and 48 will be evaluated.

### **5.3.7 Pharmacodynamic Variables**

#### **In-Vivo Biomarkers**

Blood samples will be collected to assess JAK activity effects on certain lymphocyte subsets including T (CD4+ and CD8+), B, NK, NKT, reticulocyte and other cell types.

Change from Baseline in in-vivo pharmacodynamic biomarkers at Weeks 6, 12, 24 and 48 will be evaluated.

### **5.4 Removal of Subjects from Therapy or Assessment**

#### **5.4.1 Discontinuation of Individual Subjects**

A subject may withdraw from the study at any time. The Investigator may discontinue any subject's participation for any reason, including an adverse event, safety concerns or failure to comply with the protocol.

Subjects will be withdrawn from the study immediately if any of the following occur:

- Clinically significant abnormal laboratory results or adverse events, which rule out continuation of the study medication, as determined by the Investigator and the AbbVie Therapeutic Area Medical Director.
- Serious infections (e.g., sepsis) which would put the subject at risk for continued participation in the trial as determined by the Investigator in consultation with the AbbVie Therapeutic Area Medical Director.
- The Investigator believes it is in the best interest of the subject.
- The subject requests withdrawal from study drug or the study.

- Inclusion and exclusion criteria violation was noted after the subject started study drug, when continuation of the study drug would place the subject at risk as determined by the AbbVie Therapeutic Area Medical Director.
- Introduction of prohibited medications or dosages when continuation of the study drug would place the subject at risk as determined by the AbbVie SDP.
- Subject is non-compliant with TB prophylaxis (if applicable) or develops active TB at any time during the study.
- The subject becomes pregnant while on study medication.
- Subject has known malignancy, except for localized non-melanoma skin cancer. Discontinuation for carcinoma in-situ of the cervix is at the discretion of the Investigator.
- Subject is diagnosed with lupus-like syndrome, multiple sclerosis or demyelinating disease (including myelitis).
- Subject is significantly non-compliant with study procedures which would put the subject at risk for continued participation as determined by the Investigator.
- Subject has failed to achieve at least 20% improvement from Baseline (RCT period) in TJC and SJC with upadacitinib as described in Section 5.1.
- Confirmed diagnosis of deep vein thrombosis, pulmonary embolus or non-cardiac, non-neurologic arterial thrombosis.
- Subject develops a gastrointestinal perforation (other than due to appendicitis or mechanical injury).

If, during the course of study drug administration, the subject prematurely discontinues study drug use, the procedures outlined for the premature discontinuation visit should be completed as soon as possible, preferably within 2 weeks of study drug discontinuation and preferably prior to the initiation of another therapy. However, these procedures should not interfere with the initiation of any new treatments or therapeutic modalities that the Investigator feels are necessary to treat the subject's condition. Following discontinuation of the study drug, the subject will be treated in accordance with the Investigator's best clinical judgment.

A final visit (a telephone call is sufficient if a site visit is not possible) will occur for all subjects participating in the OLE study, approximately 30 days after the last dose of study medication to determine the status of any ongoing AEs/SAEs or the occurrence of any new AEs/SAEs.

During the COVID-19 pandemic, it has been necessary to employ mitigation strategies to enable the Investigator to ensure subject safety and continuity of care.

During a state of emergency or pandemic situation like COVID-19, the Investigator should contact the sponsor TAMD before discontinuing a subject from the study or study drug for a reason other than "planned per protocol," to ensure all acceptable mitigation steps have been explored.

All attempts must be made to determine the date of the last study drug dose and the primary reason for premature discontinuation. The information will be recorded on the appropriate eCRF page.

For subjects that are considered lost to follow-up, reasonable attempts must be made to obtain information on the final status of the subject. At a minimum, two phone calls must be made and one certified letter must be sent and documented in the subject's source documentation.

Subjects who discontinue the study prematurely will not be replaced.

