**Malignancy:** Subjects who develop malignancy other than NMSC or carcinoma in situ of the cervix must be discontinued from study drug. Information including histopathological results should be queried for the confirmation of the diagnosis. Periodic skin examination is recommended for subjects who are at increased risk for skin cancer.

**Muscle-related symptoms:** If a subject experiences symptoms suggestive of myositis or rhabdomyolysis consider checking CPK and aldolase, with clinical management and/or study drug interruption as deemed appropriate by the treating physician.

**ECG Abnormality:** Subjects must be discontinued from study drug for an ECG change considered clinically significant and with reasonable possibility of relationship to study drug OR a confirmed absolute QTcF value > 500 msec.

**Management of Select Laboratory Abnormalities:** For any given laboratory abnormality, the Investigator should assess the subject, apply the standard of care for medical evaluation and treatment, following any local guidelines. Specific toxicity management guidelines for abnormal laboratory values are described in [Table 5](#) (confirmation by repeat testing is required) and may require an appropriate supplemental eCRF to be completed. All abnormal laboratory tests that are considered clinically significant by the Investigator will be followed to a satisfactory resolution. If a repeat test is required per [Table 5](#), the repeat testing must occur as soon as possible.

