6.4 Protocol Deviations

Protocol deviations based on ICH deviation criteria are categorized as follows:

1. Those who entered the study even though they did not satisfy the entry criteria
2. Those who developed withdrawal criteria during the study and were not withdrawn
3. Those who received the wrong treatment or incorrect dose, and
4. Those who received an excluded or prohibited concomitant medication.

The protocol deviations listed above will be summarized and listed by treatment group sequence (defined in Section 9.1) as well as overall for the Open-Label Treated Population.

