10.2.4 Frequent Adverse Events by System Organ Class and Preferred Term

TEAEs occurring at ≥ 2 E/100PY in any of the exposure groups will be summarized by MedDRA PT in decreasing rate.

10.2.5 Adverse Events of Special Interests Rates per 100 Patient-Years of Study Drug Exposure

The Adverse Events of Special Interests (AESI) categories will be summarized and presented for each exposure group using SOC and MedDRA PT. The AESI categories will be identified per Standard MedDRA Queries (SMQs)/Company MedDRA Queries (CMQs) in [Table 5](#) below. Adjudicated cardiovascular events will be summarized and presented by treatment groups using CAC adjudicated categories.

Table 5. AESI for Upadacitinib with SMQs/CMQs/PTs Searches

AESI	Type of MedDRA Query	Broad or Narrow Search	SMQ/CMQ Search Criteria
Serious Infections	CMQ		"Infections" – Subset for SAEs
Opportunistic Infection excluding Tuberculosis and Herpes Zoster	CMQ		"Opportunistic Infection excluding Tuberculosis and Herpes Zoster"
Possible Malignancy	SMQ	Narrow	"Malignancies"
Malignancy	SMQ		"Malignant tumours"
Non-Melanoma Skin Cancer (NMSC)	SMQ	Narrow	Skin Malignant tumours (Narrow SMQ) removing Melanoma CMQ
Malignancy excluding NMSC			"Malignant tumours" SMQ removing NMSC output
Lymphoma	SMQ		"Malignant Lymphomas"
Hepatic Disorder	SMQ	Narrow	"Drug Related Hepatic Disorders"
Adjudicated Gastrointestinal Perforations	Output from adjudication		
Anemia	CMQ		"Non-Hemolytic and Non-Aplastic Anemias"
Neutropenia	CMQ		"Hematological Toxicity – Neutropenia"
Lymphopenia	CMQ		"Hematological Toxicity – Lymphopenia"
Herpes Zoster	CMQ		"Herpes Zoster"
Creatine Phosphokinase (CPK) Elevation	PT		Search only for the PT of "Blood creatine phosphokinase increased"
Renal Dysfunction	SMQ	Narrow	"Acute Renal, Failure"
Active Tuberculosis	CMQ		"Active Tuberculosis"
Adjudicated Cardiovascular Events	Output from CAC		
MACE*			
Cardiovascular Death			
Non-fatal Myocardial Infarction			
Non-fatal Stroke			

Table 5. AESI for Upadacitinib with SMQs/CMQs/PTs Searches (Continued)

AESI	Type of MedDRA Query	Broad or Narrow Search	SMQ/CMQ Search Criteria
Undetermined/Unknown Cause of Deaths			
Other Cardiovascular events			
Adjudicated Thrombotic Events	Output From CAC		
Venous Thromboembolic Events**			
Deep Vein Thrombosis			
Pulmonary Embolism			
Other Venous Thrombosis			
Arterial Thromboembolic Events (non-cardiac, non-neurologic)			

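### The malignancy stopping rules in Protocol Sections 5.4.1 and 6.10 exempt different sets of non-melanoma skin cancer, so non-localized disease is a mandatory stop in one section and not in the other

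*Protocol*

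**What the plan says.** Two parts of the current protocol say when a malignancy ends treatment.

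- **Section 5.4.1 (Discontinuation of Individual Subjects)** opens its list with "Subjects will be withdrawn from the study immediately if any of the following occur". One item on the list is "Subject has known malignancy, except for localized non-melanoma skin cancer". The next sentence deals with a second case: "Discontinuation for carcinoma in-situ of the cervix is at the discretion of the Investigator".
- **Section 6.10 (Toxicity Management), malignancy paragraph:** "Subjects who develop malignancy other than NMSC or carcinoma in situ of the cervix must be discontinued from study drug". NMSC stands there without any qualifier. The paragraph does not refer back to 5.4.1.

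Three other places bear on the point.

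- Protocol Section 6.4 names malignancy of every type as an adverse event of special interest and points the reader to Section 6.10 for its management.
- Protocol Section 7.0 gives, as an example of a protocol deviation, a subject who met withdrawal criteria and stayed in. SAP Section 6.4 makes this a reported category: "Those who developed withdrawal criteria during the study and were not withdrawn".
- The abbreviation NMSC is missing from the protocol's list of abbreviations. SAP Table 5 spells it out in its row for "Non-Melanoma Skin Cancer (NMSC)".

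**The concern.** A mandatory stopping rule should have the same scope wherever it appears. Here one statement limits the exempt skin cancers to localized disease and the other does not. The two part company only for skin cancer that has gone beyond localized disease, which is the more serious form, in subjects on long-term treatment with a drug that acts on the immune system.

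The protocol's own signposting makes the mismatch matter in practice. A site that records a malignancy as an event of special interest is directed to 6.10, reads the wider exemption there, and finds nothing to suggest that a narrower one exists elsewhere.

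Two things are at stake: whether sites handle such a subject in the same way, and whether a subject kept on drug in reliance on 6.10 is later reported as a protocol deviation.

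**Working it through.** No sample size, power or other figure is involved, so there is nothing to recompute. The check is to set the two rules side by side and run each type of malignancy through both.

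| Event | Section 5.4.1 | Section 6.10, malignancy paragraph | Result |
|---|---|---|---|
| Localized NMSC | Exempt | Exempt | Agree |
| Metastatic or otherwise clearly non-localized NMSC | Mandatory stop | No mandatory stop | **Differ** |
| Carcinoma in situ of the cervix | Investigator decides | No mandatory stop | Compatible |
| Any other malignancy | Mandatory stop | Mandatory stop | Agree |

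Only the second row fails.

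Next, does anything else in the documents close the gap?

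1. *A definition.* Neither document defines localized, and neither narrows NMSC to localized disease for the purposes of 6.10.
2. *Precedence.* No section says that 5.4.1 overrides 6.10, or the reverse.
3. *Status of the text.* Both sentences are operative protocol text, not entries in the summary of changes.
4. *Local variants.* The United Kingdom requirements in Appendix N replace a laboratory exclusion criterion and the laboratory toxicity table. They do not touch malignancy.

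Finally, the consequence for reporting. Suppose a subject has metastatic NMSC and the site, relying on 6.10, continues study drug. The subject has met a 5.4.1 criterion and was not withdrawn. That fits the Section 7.0 example and falls in the SAP Section 6.4 category, which is summarized and listed by treatment group sequence and overall. The site would be recorded as deviating although it had followed the section to which the protocol sent it.

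**The case against.** The strongest reply is that the two rules can be obeyed together. Section 6.10 lists who must stop; it does not say that a subject with NMSC must, or even may, continue. Withdrawing a subject with non-localized NMSC under 5.4.1 breaches nothing in 6.10. Section 7.0 holds the investigator to all protocol requirements, so silence in 6.10 does not release a site from 5.4.1. Section 5.4.1 also allows withdrawal in the subject's best interest, and for adverse events judged to rule out continued treatment. All of this stands. It limits the point to what is mandatory, and to whether a reader of 6.10 would know it.

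Four stronger readings are tempting, and the documents do not support them.

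- *The sections demand opposite handling.* They do not, for the reason just given.
- *The conflict covers any invasive skin cancer.* Section 5.4.1 turns on the word localized, which is undefined, and a locally invasive tumour might still be called localized. Only metastatic or otherwise clearly non-localized disease is a clean case.
- *The sections also conflict on the action, withdrawal from the study against stopping study drug.* The same difference in wording appears for gastrointestinal perforation, which the summary of changes says was revised for consistency with 6.10, and for active tuberculosis. Section 5.4.1 sends subjects who stop study drug early to the premature discontinuation visit and gives every subject a contact about 30 days after the last dose; Section 5.1 names the same visit for those who leave the study early. This is a general habit of wording, not a malignancy problem.
- *The mismatch distorts the SAP's malignancy rates.* The category that leaves out NMSC does so by its definition in Table 5, whichever stopping rule applies. NMSC has its own row, and the overall malignancy row does not remove it.

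**Conclusion.** The point holds in a limited form. The NMSC exemption is narrower in Section 5.4.1 than in Section 6.10, and for metastatic or otherwise clearly non-localized NMSC that difference decides whether stopping is mandatory. It also decides whether a subject kept on drug counts as a withdrawal-criteria deviation.

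The size is small. The study enrolled 494 subjects for approximately 312 weeks of treatment, but those figures describe the population and not the number affected. The documents give neither the frequency of NMSC nor the share that is non-localized, so no count can be derived. That few subjects will be affected is a judgement.

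The conclusion assumes that NMSC in the protocol means what SAP Table 5 says it means, and that localized in 5.4.1 was meant to exclude something. It does not depend on any view of which clinical rule is right. The change should be made because the passage is a mandatory safety stopping rule and the correction costs almost nothing.

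**What to change.** Reconcile the two passages so that the scope of the NMSC exemption is the same in Sections 5.4.1 and 6.10. The sponsor decides which scope applies; this review does not propose one. If the localized qualifier is kept, a short definition would remove the remaining doubt about borderline tumours. It would also help to add NMSC to the protocol's abbreviation list and to put a cross-reference to 5.4.1 in the 6.10 malignancy paragraph.

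The cost is a few words in one or both sections at the next amendment. No SAP analysis has to change. The summary of changes shows that the sponsor has already made this kind of alignment between the same two sections for gastrointestinal perforation.
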